[figure not shown]
[figure not shown]
ORGANIZATION OF DETAILED PROTOCOL

Title: Effects of contralesional repetitive magnetic stimulation combined with fluoxetine on motor recovery in stroke patients
Protocol #:2014P001046
Date: 08/10/2017

[figure not shown]

Aim 1: Determine whether low-frequency rTMS of the unaffected M1 associated with fluoxetine offers an additional benefit on motor function over pharmacotherapy (fluoxetine) alone after three months of the combined therapy. Our hypothesis is that low-frequency rTMS combined with fluoxetine will induce greater improvement in motor function as compared to sham rTMS and fluoxetine.

Sub Aim 1.1: As to control for the effects of spontaneous recovery, we will also assess whether the superior effects of the combined effects will be superior to spontaneous recovery by comparing the results of the two groups against a placebo group (placebo fluoxetine and sham rTMS). We hypothesize that both groups (combined treatment and fluoxetine alone) will have a superior effect as compared to placebo only.

Aim 2: Determine whether fluoxetine combined with rTMS results in additional positive modulation of motor cortex excitability and cortical plasticity as compared to fluoxetine alone. Our hypothesis is that active rTMS combined with fluoxetine will induce a greater increase in the amplitude of motor evoked potential and greater LTP-like (long-term potentiation) as indexed by PAS-25 of the affected hemisphere (M1) as compared to sham rTMS combined with fluoxetine.

V. SUBJECT SELECTION

We will recruit 45 patients with ischemic stroke. The desired sample size is calculated, with some assumptions, based on the amount of patients treated in Spaulding Rehabilitation Hospital and affiliate hospitals and clinics. The study eligibility criteria that will be used for this study are based on the FLAME trial (as we will investigate the additional benefits of combining fluoxetine with rTMS). We broadened the motor score criteria and time since stroke in order to significantly improve the impact of the study and improve our understanding of the mechanisms behind plasticity after stroke in a broad population.

Subjects will conform to the following criteria:

Inclusion Criteria:

- Ischemic infarction within the past 2 years post event that has caused hemiparesis or hemiplegia, as self-reported and/or confirmed by medical record.
- Older than 18 years old.

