For the first aim, the primary outcome will be motor function changes as indexed by Jebsen Taylor Hand Function test and secondary outcome will be Fugl-Meyer motor scores. Differences between the two groups will be tested using Student's t-test and, in addition, we will adjust for important baseline variables and also test the time effect in general mixed longitudinal models. Secondary analyses will be conducted in an exploratory manner (no correction for multiple comparisons). [We will also conduct exploratory correlational analysis as to understand whether beneficial effects of the combined intervention (active rTMS and fluoxetine) are associated with any baseline characteristics as to explore potential predictors of the effects of treatment. This result may also be used along with results for aim 2 to understand the mechanisms of the combined treatment.]

[For subaim 1: the primary outcome will be motor function changes as indexed by Jebsen Taylor Hand Function test and secondary outcome will be Fugl-Meyer motor scores. We will conduct the same analysis as aim 1 (Differences between the two groups will be tested using Student's t-test with adjustment for covariates) but in this case we conduct two comparisons (real rTMS+fluoxetine vs. sham rTMS+placebo fluoxetine and sham rTMS+fluoxetine vs. sham rtMS+placebo fluoxetine)]

For the second aim, we will initially build a mixed ANOVA model in which the dependent variable will be the parameters of cortical excitability and plasticity (PAS) indexed by

neuropsychological measures. The independent variables will be group [(active and placebo control)], time and the interaction group/time. [If we find a significant interaction effect between group and time, we will confirm our hypothesis that TMS induces a significant differential plasticity when compared to fluoxetine alone. Furthermore we will conduct additional analysis in which we will change the groups in the variable group (real rTMS+fluoxetine vs. sham rTMS+placebo fluoxetine and sham rTMS+fluoxetine vs. sham rtMS+placebo fluoxetine)

	·

Adeyemo, B. O., Simis, M., Macea, D., & Fregni, F. Systematic Review of Parameters of Stimulation: Clinical Trial Design Characteristics and Motor Outcomes in Noninvasive Brain Stimulation in Stroke. *Frontiers in Psychiatry*, *3*, 8.

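### Does Sub Aim 1.1 need a rule for the case where only one of its two placebo comparisons is significant?

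*Combined protocol and SAP*

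**What the plan says.** In the aims at the front of the combined protocol and SAP, Sub Aim 1.1 has two sentences. The first gives the purpose: "we will also assess whether the superior effects of the combined effects will be superior to spontaneous recovery". It goes on to say that this is done by comparing the two treated groups with a placebo group. The second gives the hypothesis: "We hypothesize that both groups (combined treatment and fluoxetine alone) will have a superior effect as compared to placebo only".

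The statistical analysis text has a paragraph for the subaim. It names the outcome ("For subaim 1: the primary outcome will be motor function changes as indexed by Jebsen Taylor Hand Function test"), with the Fugl-Meyer score as secondary, carries over the Aim 1 method (Student's t-test with covariate adjustment), and adds: "in this case we conduct two comparisons (real rTMS+fluoxetine vs. sham rTMS+placebo fluoxetine and sham rTMS+fluoxetine vs. sham rtMS+placebo fluoxetine".

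Two neighbouring statements bear on the point. The Aim 1 paragraph says: "Secondary analyses will be conducted in an exploratory manner (no correction for multiple comparisons". The Aim 2 paragraph says which finding counts as confirmation ("If we find a significant interaction effect between group and time, we will confirm our hypothesis that TMS induces a significant differential plasticity") and then turns to the placebo contrasts: "Furthermore we will conduct additional analysis in which we will change the groups in the variable group".

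**The concern.** Read quickly, the subaim seems to have two success criteria. The purpose sentence makes the combined effect the thing that must beat spontaneous recovery. The hypothesis sentence adds fluoxetine alone. If the combination beats placebo and fluoxetine alone does not, the first looks met and the second is not. The subaim paragraph has no counterpart to the Aim 2 confirmation sentence, and it is not clear whether the exploratory, no-correction sentence covers it.

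The worry is that the word supported could be applied or withheld after the data are seen. If fluoxetine alone did nothing and the combination worked by 0.8 SD, the looser reading could call the subaim supported in most trials where the combination is significant, although half of its hypothesis would be false.

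**Working it through.** **Step 1: the sentences side by side.**

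- Purpose sentence: its grammatical object is the combined effect, but its method is a comparison of both groups with placebo: "whether the superior effects of the combined effects will be superior to spontaneous recovery by comparing the results of the two groups".
- Hypothesis sentence: both groups beat placebo.
- Analysis: combination vs placebo, and fluoxetine alone vs placebo.

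The method, the hypothesis and the tests all cover the same two groups. Only the object of the purpose sentence is narrower. That is loose drafting of a question, followed by one hypothesis and two matching tests.

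**Step 2: which result patterns are affected.** There are four.

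| Combination vs placebo | Fluoxetine alone vs placebo | Combination-only reading | Both-groups reading |
|---|---|---|---|
| significant | significant | supported | supported |
| not | not | not supported | not supported |
| not | significant | not supported | not supported |
| significant | not | supported | not supported |

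The readings part in the last row only. Under either reading the two contrasts are the same, with the same estimates and tests.

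**Step 3: how often the last row occurs.** Inputs from the document: 45 patients, 15 per group (Study overview); 3 × 15 = 45 agrees. The text shown gives no alpha, sidedness, effect size or SD, so no power figure can be reproduced. Assumptions: two-sided 0.05 per test, equal SDs, all 15 per arm analysed, no covariates, and only results favouring treatment counted.

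Each test is a pooled t-test with 15 + 15 − 2 = 28 degrees of freedom. For a true difference of d SD the noncentrality is d × √(15/2) = 2.739d. The two tests share the placebo arm, so their joint behaviour was simulated (400,000 trials per scenario). The split is

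P(combination significant, fluoxetine alone not) = P(combination significant) − P(both significant).

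Worked case, combination 1.0 SD and fluoxetine alone 0.5 SD over placebo: 0.754 − 0.242 = 0.512, or 51%. The exact noncentral t value for the combination comparison is 0.753, which agrees with the simulation.

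Other pairs that keep the hypothesised order (combination above fluoxetine alone, fluoxetine alone above placebo):

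| Combination, SD | Fluoxetine alone, SD | Split |
|---|---|---|
| 0.2 | 0.1 | 6% |
| 0.6 | 0.3 | 27% |
| 0.8 | 0.5 | 35% |
| 1.0 | 0.5 | 51% |
| 1.5 | 1.0 | 23% |
| 2.0 | 1.5 | 2% |
| 1.8 | 0.2 | 92% |

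The split is rare when both effects are very small or both very large, and frequent when they lie far apart. With fluoxetine alone null and the combination at 0.8 SD, the split is 54% and both are significant in 2.3%.

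**Step 4: is there an error-rate problem?** With all arms equal, at least one placebo comparison is falsely superior in 4.6% of trials and both in 0.5%. Requiring both, as the hypothesis sentence does, is the stricter reading and needs no alpha adjustment.

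**The case for a change.** The best case for acting is this. Aim 2 has a sentence on what confirms its hypothesis and the subaim has none. The subaim has its own named primary outcome, so it does not plainly fall under the exploratory sentence. A split is a likely result over a good part of the plausible effect range. The choice of reading also matters to the label: at 1.0 and 0.5 SD, combination vs placebo alone succeeds in 75% of trials and both comparisons in 24%. A sentence or two would settle it at no cost in tests or sample size.

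Much of this stands. No sentence in the text shown says how a split is described, and the figures reproduce. Three things limit it:

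- The hypothesis sentence already supplies the natural rule, since a claim that both groups beat placebo is not met when one does not.
- Aim 2 is a weaker model than it seems. It calls the placebo contrasts additional, without saying whether they are exploratory, supportive or uncorrected.
- Parts of the protocol are not public, so wording on alpha or on the status of these comparisons may exist elsewhere.

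**Conclusion.** No change is needed. The gap is real but small, and an analyst would fill it sensibly: report combination vs placebo and fluoxetine alone vs placebo separately on the Jebsen Taylor test, and judge the hypothesis by what it says, which is both groups. A reader shown the two results would see at once if fluoxetine alone had not been shown to beat placebo. What is open is one summary word for a sub-aim, in one of four result patterns. Aim 1 compares the combination with fluoxetine alone in a single contrast and is untouched.

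The frequency of that pattern does not alter this. It runs from about 2% to over 90% under the plan's own ordering, assuming 15 analysed per arm, two-sided 0.05 and unadjusted t-tests, and the documents give no effect size to choose within that range. Covariate adjustment, which the plan intends, would shift the figures but not the reasoning.

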- Upper extremity weakness defined as a score of >11 and ≤56 on the arm motor Fugl-Mayer motor scale.
- Minimal pre-stroke disability defined as a score of <3 in the Modified Rankin Scale.
- Subjects need to be able to follow directions and participate in 2 hours of testing with short breaks.
- Subjects need to be able to provide informed consent.

[figure not shown]
Exclusion Criteria:

- Any substantial decrease in alertness, language reception, or attention that might interfere with understanding instruction for motor testing
- Excessive pain in any joint of the paretic extremity (not applicable to severe stroke subjects), as self reported
- Contraindications to single pulse TMS (will be used to measure cortical excitability) such as: history of seizures, unexplained loss of consciousness, any metal implants in the head, frequent or severe headaches or neck pain, any other electronic implanted medical devices such as pacemakers, defibrillators, or implant medication pump.

- Patients who are currently taking fluoxetine should accept a 5 week washout period before baseline (to be reconfirmed during baseline visit).
- Patients taking any other SSRI at the time of enrollment or in the previous month (the patients should accept a 5 week washout period before baseline to be reconfirmed during baseline visit).
- Patients taking any other medication likely to have adverse interaction with SSRIs (all the medications the patient is taking will be carefully reviewed, as noted below in "Monitoring of important drug interactions").
- Active depression on admission to SRH defined by a score of 24 or higher in the Hamilton Depression Rating Scale (HAM-D)
- Concurrent medical condition likely to worsen patient's functional status in the next 6 months such as: cancer, terminal heart, kidney or liver disease, as self-reported and/or confirmed by medical record.
- Pregnancy.

VII. STUDY OVERVIEW AND PROCEDURES

Study overview:

This study is a parallel, randomized, double blind, placebo controlled clinical trial. We will use the same duration and regimen of fluoxetine treatment as the FLAME trial as this trial showed that fluoxetine is efficacious when compared against placebo. Subjects will be randomized to one of three groups, where they will receive: 1) fluoxetine + active rTMS, 2) fluoxetine + sham rTMS or 3) sham rTMS + placebo fluoxetine. With a total of 45 patients, 15 patients will be randomized to each group using a computer based randomization program.

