This study is structured in 3 visits where baseline and post intervention assessments will be collected, 10 daily stimulation sessions (from 3^{rd} until 12^{th} visit), and subsequently, subjects will return for a weekly stimulation session for the next 8 weeks (visit 14^{th} to 21^{th}). Last visit will be the 22^{nd} and the whole battery of assessments is going to be collected. A table of the study flow is presented below.

Protocol Details:

There will be ten stimulation visits (to be given over a period of 15 days), followed by weekly sessions of stimulation for the next 8 weeks. During each stimulation visit, rTMS equipment will be placed on the subject's unaffected hemisphere over the primary motor cortex (M1). They will receive either active or sham rTMS with fluoxetine – or sham rTMS and placebo. The 30 subjects randomized to receive sham rTMS will have the opportunity to enroll into an open label at the conclusion of their participation in the randomized portion of the trial. This will consist of 10 daily active stimulation sessions that can be carried out over the course of 2 weeks. Subjects will only receive rTMS and not the study drug, Fluoxetine.

Intervention Details:

Repetitive transcranial magnetic stimulation:

Low frequency rTMS stimulation (active stimulation)

• During this stimulation session, the participant will receive a session of low-frequency rTMS to the primary motor cortex of the unaffected cerebral hemisphere. The resting motor threshold (MT) of the first dorsal interosseous (FDI) in the affected and unaffected hemispheres will be measured. The participants will receive the rTMS over the area corresponding to the "hot spot" for stimulation as defined by motor threshold determination, as described by prior rTMS application studies (Rossini et al., 1994).

• Low frequency rTMS stimulation will be applied according to the following parameter: intensity of 100% MT, frequency of 1 Hz, 1200 pulses as a single, continuous train lasting 20 minutes. This intervention is associated with significant motor gains in chronic (Mansur, 2005)(Fregni, 2006) and acute stroke. In addition, it is a safer approach to be used in chronic stroke (Fregni review).

Sham rTMS stimulation:

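### Aim 2 rests on a mixed ANOVA group-by-time test that uses baseline as an outcome; adjusting for baseline and keeping every available TMS assessment would be a modest, low-cost gain

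*Combined protocol and SAP*

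**What the plan says.** The analysis text for the second aim states: "we will initially build a mixed ANOVA model in which the dependent variable will be the parameters of cortical excitability and plasticity (PAS". The independent variables are group, time and group by time; no baseline covariate is listed. The decision rule is "If we find a significant interaction effect between group and time, we will confirm our hypothesis". The Aim 2 hypothesis is directional: "active rTMS combined with fluoxetine will induce a greater increase in the amplitude of motor evoked potential", with a matching statement for the PAS-25 response. It names no time point.

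For Aim 1, by contrast, the plan adjusts for baseline variables and will "also test the time effect in general mixed longitudinal models". No covariance structure or treatment contrast is given there either.

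On timing, the description of visits says "This study is structured in 3 visits where baseline and post intervention assessments will be collected". The available text does not list which visits carry TMS and PAS. The section on cortical excitability describes MEPs recorded before and after stimulation, which could mean two time points. It also sets TMS intensity so that baseline MEP is about 1 mV.

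On size, "With a total of 45 patients, 15 patients will be randomized to each group using a computer based randomization program". The available text gives no effect size, SD, correlation, alpha, dropout rate or missing-data rule for Aim 2.

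**The concern.** Three features of the Aim 2 test deserve attention.

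- **Baseline is an outcome.** With only group and time in the model, baseline enters as a level of time. The test then works on departures from each patient's own mean. That is less efficient than adjusting for baseline when the within-patient correlation is moderate.
- **Missed assessments.** A classical repeated-measures fit needs a complete time course. Under an assumed 10% missing at each of two follow-ups, 15 × 0.9 × 0.9 = 12.15 patients per arm remain, against 15 × 0.9 = 13.5 with a final assessment. A completers-only analysis generally also relies on data being missing completely at random.
- **No direction.** With three time points the interaction is a 2-df F test. A divergence in the wrong direction would satisfy the stated rule as well as one in the hypothesised direction.

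The Aim 2 comparison has 30 patients, so efficiency lost here is hard to recover elsewhere.

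**Working it through.** **Plan's own figure.** 3 × 15 = 45 agrees with "We will recruit 45 patients with ischemic stroke". The stated basis is feasibility ("The desired sample size is calculated, with some assumptions, based on the amount of patients treated in Spaulding Rehabilitation Hospital"), so there is no Aim 2 power figure to reproduce.

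**Inputs.** From the document: n = 15 per arm, two arms. Assumed: two-sided alpha 0.05; three time points; equal variances and equal correlation ρ between times; peak effect 0.8 SD. Effects at the middle and final visits, in SD: growing 0.4, 0.8; sustained 0.8, 0.8; late 0, 0.8; waning 0.8, 0.4. The baseline effect is 0.

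**A. Planned mixed ANOVA interaction, complete data.** λ = (n/2) × Σ(δt − mean δ)² / (1 − ρ), on 2 and 2 × 28 = 56 df. Growing: the mean is 0.4 and the sum of squares is 0.16 + 0 + 0.16 = 0.32. At ρ = 0.4, λ = 7.5 × 0.32 / 0.6 = 4.00. Sustained and late both have a sum of squares of 0.4267.

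**B. Baseline as covariate, joint test over the two post-baseline visits.** Given baseline, each visit has variance 1 − ρ² and the two visits have covariance ρ − ρ². Then λ = (n/2) × δ′V⁻¹δ × 28/29, where 28/29 is the average allowance for chance baseline imbalance. The df are 2 and 26 (30 − 3 = 27 error df, less 1 for an unstructured 2 × 2 covariance; baseline slope free at each visit). Growing at ρ = 0.4: V has 0.84 on the diagonal and 0.24 off it. δ′V⁻¹δ = (0.84 × 0.80 − 2 × 0.24 × 0.32) / (0.84² − 0.24²) = 0.5184 / 0.648 = 0.80. So λ = 7.5 × 0.80 × 28/29 = 5.79.

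| ρ | Shape | λ for A | Power A | λ for B | Power B | Difference (points) |
|---|---|---|---|---|---|---|
| 0.4 | growing or waning | 4.00 | 39.6% | 5.79 | 51.7% | +12.1 |
| 0.4 | sustained | 5.33 | 50.8% | 8.58 | 69.6% | +18.8 |
| 0.4 | late | 5.33 | 50.8% | 6.01 | 53.3% | +2.5 |
| 0.6 | growing or waning | 6.00 | 56.0% | 7.37 | 62.5% | +6.5 |
| 0.6 | sustained | 8.00 | 69.3% | 10.53 | 78.8% | +9.5 |
| 0.6 | late | 8.00 | 69.3% | 8.43 | 68.7% | −0.6 |
| 0.8 | growing or waning | 12.00 | 86.5% | 12.92 | 86.8% | +0.3 |
| 0.8 | sustained | 16.00 | 94.6% | 17.82 | 95.5% | +0.9 |
| 0.8 | late | 16.00 | 94.6% | 16.04 | 93.2% | −1.4 |

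Simulation at ρ = 0.4 agrees within its error of about 1.5 points. B against A was 51 vs 39 (growing), 70 vs 52 (sustained), 51 vs 39 (waning) and 54 vs 52 (late), with B's type I error about 5%.

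**Model class alone.** This compares the same group-by-time test, with baseline still an outcome, fitted by complete-case ANOVA and by a REML random-intercept model (ρ = 0.5, sustained effect unless stated).

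- Complete data: 59.7% and 59.7%.
- One patient per arm (7%) missing the middle visit: 55% to 59%.
- Two per arm missing one visit: 51% to 57%.
- Three per arm (20%) missing one visit: 47% to 56%.
- Three per arm lost after baseline: a gain of only 1 to 4 points across effect shapes.

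Across scenarios and shapes the range is about 1 to 9 points. It is a guide only for model B, where a patient with no post-baseline assessment adds nothing.

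**Two time points only.** The interaction is then the t-test on change: λ = 7.5 × 0.64 / (2 × 0.5) = 4.8 at ρ = 0.5, power 56.2%. Baseline-adjusted ANCOVA has λ = 7.5 × 0.64 / 0.75 = 6.4, power 68.4% (66.9% after the 28/29 allowance). At ρ = 0.7 the figures are 77.9% and 84.1% (82.8%).

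**Final visit as the sole test.** λ = 7.5 × δ² / (1 − ρ²) × 28/29 on 1 and 27 df, with δ the final-visit effect. At ρ = 0.6, a growing effect gives 7.5 × 0.64 / 0.64 × 28/29 = 7.24, power 73.7% against 56.0% for the interaction. A waning effect gives 7.5 × 0.16 / 0.64 × 28/29 = 1.81, power 25.5% against 56.0%.

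**The case against.** The strongest reply is that mixed ANOVA is a valid test with nominal type I error, and that this is an efficiency preference for a mechanistic aim. That is fair, and it limits the weight of the point.

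A reader might infer more than the documents support in three ways.

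- **That the mixed model named for Aim 1 would give clearly more power at no cost.** It would not. With complete balanced data under equal correlation, it gives the same F for group by time. Moreover, the Aim 1 text names that model to test the time effect, with no contrast or covariance structure.
- **That the test belongs at visit 22 alone.** Only Aim 1 specifies three months; Aim 2 names no time point. Stimulation is front-loaded (ten daily sessions, then weekly for 8 weeks), so a waning effect is possible, and a sole final-visit test would then lose about half the power.
- **That the plan commits to dropping incomplete patients.** It does not say so. A mixed ANOVA can be fitted by likelihood, and the Aim 2 text breaks off inside an open bracket, so a missing-data rule may stand in text not available here.

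Two further objections stand as limits. Three time points is an assumption; with two, nothing is spread over time and sphericity does not arise. For MEP amplitude, one of the two measures in the hypothesis, fixing baseline near 1 mV leaves little for a covariate to explain. With a near-constant baseline, simulated ANCOVA and simple change at the final visit were equal to within about a point (54–55% and 55–56%).

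What the reply does not remove is that no baseline covariate is listed for Aim 2, and that the decision rule has no sign.

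**Conclusion.** The point holds as a modest efficiency and specification improvement. Taking baseline as a covariate and testing the treatment difference jointly over post-baseline visits gains about 2 to 18 points of power at correlation 0.4, 0 to 10 at 0.6 and near zero at 0.8. In the calculations its worst loss is 1.4 points (late effect, correlation 0.8). Keeping patients with a missed visit may add roughly 1 to 9 points if 7 to 20% miss one, and nothing if none do.

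These sizes rest on assumed effect size, effect shape, correlation, missingness and number of TMS assessments, none of which the available text settles. The gain applies mainly to measures whose baseline varies freely, such as PAS response, motor threshold, and paired-pulse and transcallosal measures. The planned test is not invalid.

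**What to change.** For each Aim 2 measure, fit a linear mixed model by REML to all available post-baseline assessments of randomised patients. Include the baseline value, group, visit and group by visit, and state the covariance structure and a small-sample df method in advance.

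Test fluoxetine + active rTMS against fluoxetine + sham rTMS jointly over the post-baseline visits. This means group and group by visit together: the group-by-visit term alone would miss a sustained effect. Report the signed difference with its confidence interval at each visit, and require the hypothesised direction before calling the hypothesis confirmed.

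State which visits carry TMS and PAS. If there are only two time points, the analysis becomes baseline-adjusted ANCOVA. If the sponsor prefers visit 22 as the sole test, it should say so in advance and accept the loss if the effect wanes.

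The cost is a rewritten analysis sentence and somewhat more modelling work. No new data are needed. The model assumes data missing at random, which should be stated.

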- 10. The Antidepresant Side-Effect Checklist (ASEC): The ASEC is a questionnaire that assesses the possible appearance of side effects related to the use of common antidepresants, their severity and if they are linked or not to the drug (Uher, 2010).
- 11. Blinding Questionnaire: to be performed at the end of the daily stimulation sessions and at the end of the weekly stimulation sessions.. This questionnaire will ask the rater and the subjects whether the intervention was sham or active rTMS. The confidence of these responses will be rated from 0 to 5 0 being no confidence and 5- total confidence. If the subject is interested in knowing what stimulation he/she received, the co-investigator may inform the subject when his/her participation in the trial has ended.

12. A log of the hours of therapy that patients are receiving and the meditations they are taking will be kept and updated every week.

Assessment of cortical excitability and plasticity – single and paired pulse TMS and PAS:

Aim 1: Determine whether low-frequency rTMS of the unaffected M1 associated with fluoxetine offers an additional benefit on motor function over pharmacotherapy.

We will investigate changes in cortical excitability by evaluating the motor evoked potential (MEP) and the resting motor threshold (MT) (with the same methods as in our previous study (Fregni et al., 2006b)). We will also measure intracortical excitability using the technique of paired-pulse, and interhemispheric differences using transcallosal inhibition. Both the affected and unaffected M1 will be studied.

We will investigate the resting motor threshold (measured following the technique described by (Rossini et al., 1994)) before and after stimulation. For the MEP study, we will initially adjust TMS intensity to achieve a baseline MEP in the first dorsal interosseous of about 1 mV peak-to-peak amplitude before intervention. Stimulation intensity will be kept constant for each subject throughout the experiment. The MEPs will be recorded and stored in a PC computer for off-line analysis. We will record 10 MEPs for each time point (immediately before and after the rTMS stimulation) and average their peak-to-peak amplitude and area-under-the-curve.

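### Aim 2's confirmation rule gives no direction or hemisphere and does not tie the interaction to MEP amplitude and PAS-25, the content of the hypothesis it is meant to test

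*Combined protocol and SAP*

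**What the plan says.** Aim 2, in the opening statement of aims, predicts for active rTMS plus fluoxetine a "greater increase in the amplitude of motor evoked potential and greater LTP-like (long-term potentiation) as indexed by PAS-25 of the affected hemisphere (M1"), relative to sham rTMS plus fluoxetine. That fixes a direction, two measures, one hemisphere and one comparator.

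The analysis paragraph for the second aim describes a mixed ANOVA in which "the dependent variable will be the parameters of cortical excitability and plasticity (PAS"), with group, time and their interaction as the independent variables. It then gives the decision rule: "If we find a significant interaction effect between group and time, we will confirm our hypothesis that TMS induces a significant differential plasticity", relative to fluoxetine alone.

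The section on assessment of cortical excitability and plasticity lists more measures than Aim 2 names: resting motor threshold, and MEPs summarised by both amplitude and area under the curve. It adds: "We will also measure intracortical excitability using the technique of paired-pulse, and interhemispheric differences using transcallosal inhibition". It also says: "Both the affected and unaffected M1 will be studied".

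Two sentences in the first-aim paragraph bear on how Aim 2 results will be read. One is "Secondary analyses will be conducted in an exploratory manner (no correction for multiple comparisons"). The other, about the exploratory correlation analysis, is "This result may also be used along with results for aim 2 to understand the mechanisms of the combined treatment".

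**The concern.** The plan does more than leave detail out. It states the condition under which a hypothesis will be declared confirmed, and that condition is looser than the hypothesis. An interaction F-test has no sign, and describing the result as differential plasticity does not supply one. The model has no hemisphere term, and the rule does not say which parameter must show the interaction.

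The hemisphere matters here because, under Protocol Details, the coil is placed over the unaffected M1. A change in excitability at the stimulated site is plausible, but it is not what Aim 2 predicts.

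At stake is the mechanistic conclusion. It could be reported as confirmed on data that contradict it, or on a measure or hemisphere it does not concern, and the plan says Aim 2 results may feed the account of how the combined treatment works.

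**Working it through.** **Text comparison**

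| Element | Aim 2 hypothesis | Confirmation rule |
|---|---|---|
| Direction | Greater with active rTMS | None |
| Measures | MEP amplitude and PAS-25 | Parameters of excitability and plasticity; PAS named in brackets, MEP amplitude not named |
| Hemisphere | Affected M1 | None |
| Comparator | Sham rTMS plus fluoxetine | Fluoxetine alone (consistent) |

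Direction and hemisphere are wholly absent. The measures are partly present: PAS is mentioned, but the PAS-25 form and MEP amplitude are not attached to the rule.

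**Size of the direction gap**

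The documents give no alpha, effect size, SD or power for Aim 2, so there is no figure of the plan's own to reproduce. The following is for scale only.

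Inputs:
- 15 patients per arm (Study overview).
- Assumed: two-sided alpha 0.05; two time points; one parameter tested; effects expressed in SDs of the change score.

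With two groups and two time points, the interaction F equals the square of the two-sample t on change scores. Degrees of freedom are 15 + 15 − 2 = 28 and the critical value is 2.048. The noncentrality for a standardised difference d is d × √(15/2) = 2.739 × d.

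If active rTMS is truly worse by d:

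| d | Noncentrality | Meets the rule as written (significant, favouring sham) | Meets it if the hypothesised direction is required |
|---|---|---|---|
| 0.5 | 1.369 | 26.2% | 0.05% |
| 0.8 | 2.191 | 56.2% | 0.002% |
| 1.0 | 2.739 | 75.3% | 0.0002% |

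With no true effect, half of the 5% error, that is 2.5%, falls in the wrong direction and still meets the rule.

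**What restricting the rule does**

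Suppose only the two hypothesised measures count, direction is required and each is tested at two-sided 0.05 without adjustment. If the tests are independent, the chance of at least one false claim in the hypothesised direction is 1 − 0.975² = 4.9%, against 2.5% for a single measure. Holm starts with the smaller p-value at 0.05/2 = 0.025, which brings this to 1 − 0.9875² = 2.5%.

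The price in power, for a true 0.8 SD effect in the hypothesised direction on one measure only: 56.2% at 0.05, and 44.1% at 0.025 (critical value 2.368).

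**The case against.** The strongest reply is that the rule refers to the investigators' own hypothesis, which is set out once, under Aim 2, with direction, measures, hemisphere and comparator. On that reading nobody would call a result favouring sham a confirmation, and the gap is only a failure to repeat. This may well be the intention. A reader might infer that the investigators plan to claim success from contrary data; nothing in the documents supports that. What stands is that the rule does not simply point back. It restates the hypothesis in weaker terms, while the assessment section supplies several other parameters in both hemispheres that could satisfy those terms.

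A second reply is that Aim 2 is exploratory anyway. The sentence on exploratory, uncorrected secondary analyses stands in the first-aim paragraph. If it covers Aim 2, promising confirmation conflicts with it; if it does not, nothing limits the rule. Either way the wording needs an edit.

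Third, PAS is named and the rule speaks of plasticity, so it is doubtful that motor threshold or paired-pulse results would be offered as confirmation. This is fair, and it narrows the point about measures. It does not touch direction or hemisphere.

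Fourth, text may be missing: a bracket around the rule never closes, no PAS procedure is shown, and the study-flow table is absent. The rule sentence itself is complete. But the choice of time contrast may be settled in text that is not visible. The assessment section describes MEPs taken immediately before and after stimulation, and the overview describes three assessment visits. No defect is claimed on that score. It does limit the figures above, which apply to two time points and not directly to an interaction over three.

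**Conclusion.** The point holds as a mismatch between the stated hypothesis and the stated rule for confirming it. It should be fixed, with medium confidence, because the rule can be met by contrary or off-target data and the correction is cheap. The textual finding needs no assumption. The 26%, 56% and 75% figures are ordinary power calculations applied to effects in the wrong direction; they rest on the assumed alpha, effect sizes and two time points, and do not predict what the trial will find.

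Three stronger readings are not supported:
- **Chance confirmation far above 5%.** A reader might infer this from the number of parameters. It would require testing each one separately and letting any single result suffice, which the text does not state.
- **Both measures must succeed.** A reader might infer this from the way Aim 2 joins the two. The wording lists two expectations and sets no joint success criterion.
- **The main result is at risk.** The Jebsen-Taylor comparison for Aim 1 is analysed separately and is not affected. The Aim 2 comparator is not in dispute either.

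**What to change.** In the second-aim paragraph, state that the Aim 2 hypothesis is supported only by an interaction for active rTMS plus fluoxetine versus sham rTMS plus fluoxetine that is significant and in the hypothesised direction, on affected-hemisphere MEP amplitude, PAS-25 or both. Report the conclusion measure by measure. Name one adjustment across the two and apply it as defined. Under Holm, for example, the smaller p-value must be at most 0.025 before the other is tested at 0.05, so two p-values between 0.025 and 0.05 support neither measure.

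Label the other excitability parameters, the unaffected hemisphere and the comparisons with the placebo arm as exploratory. Replace the bracketed group label, which speaks only of active and placebo control, with the names of the two arms compared.

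The cost is wording only, with no new measurements. Positive findings on other parameters become exploratory. The adjustment also costs some power: at an assumed 0.8 SD and 15 per arm, about 44% instead of 56% when only one of the two measures responds.
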